Tranexamic acid's role in treating hemorrhage have been widely studied in non-pregnant populations. Studies of TXA in obstetrics are limited. The American College of Obstetricians and Gynecologists believes the data is insufficient to recommend tranexamic acid for prophylaxis⁹.

We designed a randomized placebo-controlled trial comparing TXA dosing prior to incision for cesarean delivery with a repeat dose given at placental delivery. Our purpose is to quantify blood loss during uncomplicated repeat cesarean deliveries with and without TXA. We elected to study scheduled elective cesareans because such procedures are at low risk for profound hemorrhage. It is our intent to have a study cohort where the two treatment groups (TXA or placebo) are as comparable as possible, so we are not testing the efficacy of TXA in women with highly variable volumes of obstetric hemorrhage. TXA here-to-for has not been studied in a context where blood volume loss was quantified in both study groups.

Specific Aims:

Specific Aim 1: To determine the efficacy of perioperative TXA administration on reducing blood loss in women undergoing scheduled repeat cesarean delivery. We will use a method for calculating blood loss previously described by our group in an observational study of 1443 women with obstetrical hemorrhage¹⁰. Using this mathematical method to calculate maternal blood volume, pre- and post-cesarean, we hypothesize that an initial bolus of TXA with a second bolus at placental delivery will reduce blood loss in comparison to placebo.

Specific Aim 2a: To quantify maternal fibrinolytic activity with and without TXA in women undergoing cesarean delivery. In vitro serum markers of fibrinolysis (fibrinogen, plasminogen activator inhibitor-1 (PAI-1), tissue plasminogen activator (t-PA), and D-dimer) and rotational thromboelastometry will be used to quantify fibrinolytic activity. Given that TXA is a lysine analog that prevents the conversion of plasminogen to plasmin, thereby inhibiting fibrinolysis⁶, we *hypothesize* that in women given TXA, will have less evidence of fibrinolysis on measurement of serum markers and rotational thromboelastometry¹¹.

Specific Aim 2b: To ascertain if TXA effects on fibrinolysis dissipate by postoperative day

1. We *hypothesize* that by postoperative day 1, effects of TXA will have dissipated, as evidenced by comparable levels of fibrinolysis (serum markers and rotational thromboelastometry) in the TXA and placebo groups.

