Methods: For plasma *in-vitro* fibrinolytic activity (To be collected before initiation of infusion of TXA or placebo, at placental delivery, and on postpartum day 1): quantitative t-PA and PAI-1 levels will be collected in a light blue top container with 3.2% sodium citrate. The specimens will be transported to the research lab, stored at -20°C, and batch testing performed when appropriate. Fibrinogen levels and D-Dimer will be collected in a blue top container with 3.2% sodium citrate. The specimen for hematocrit will be collected in a lavender container.

For rotational thromboelastometry (ROTEM™), (To be collected before initiation of infusion, TXA or placebo, at delivery, and on postpartum day one): a small aliquot of venous blood will be added to a disposable cuvette (measuring cell) in a heated cuvette holder. A disposable pin (sensor) fixed to a rotating shaft rotates back and forth 4.75 degrees. The exact position of the shaft is detected by reflection of light on a small mirror on the shaft. Data obtained from the reflected light is then computer processed into a graphical output with numerical values reported.

On ROTEM™ analysis, we will compare ML values at 60 minutes, CT, CFT, and MCF values, numerically and graphically. Normal levels are graphically depicted in **Fig. 4**, fibrinogen deficiency in **Fig. 5**, and hyperfibrinolysis in **Fig. 6**.

[figure not shown]

Fig. 4. Normal levels on ROTEM™.

[figure not shown]

Fig 5. Fibrinogen deficiency on ROTEM™.

[figure not shown]

Fig. 6 Hyperfibrinolysis on ROTEM™.

Sources of Research Material: There are two electronic data sets to be used in this proposed study:

- 1) The Epic Electronic Medical Record (EMR) system at Parkland Hospital provides an integrated EMR system. Patient data is entered through a menu driven, formatted data entry screen and may be reviewed through similar processes. It was implemented at Parkland April 28, 2009. Epic is managed by Information Technology at Parkland and maintains strong security.

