- 2) Selected obstetrical outcomes for all women who give birth at Parkland Hospital, as well as neonatal outcomes, are entered into a computerized obstetric database. Nurses attending each delivery complete an obstetrical data sheet, and research nurses assess the data for consistency and completeness before they are stored electronically. Data on neonatal outcomes are abstracted from discharge records. These data are stored on a secure file server maintained by the Department of Obstetrics and Gynecology.

Recruitment Methods and Consenting Process: Women scheduled for elective cesarean delivery Monday through Friday at Parkland Labor and Delivery and who meet the inclusion criteria will be eligible to participate. A research nurse will screen all women that meet study criteria. After identification of a potential subject, the principal investigator will discuss the research protocol, answer any questions, and obtain consent and HIPAA authorization. Consents will be available in English and Spanish, and an interpreter will be available.

Potential Risks:

	Frequent (30% of subjects)	Uncommon (<15% of subjects)
Major		Tranexamic acid: 
 • Hypotension (rare) • Thromboembolism (Maternal AND fetal) (rare) • Seizures (rare) • Anaphylaxis (rare) Venous blood draw: 
 • Excessive bleeding (rare) • Infection (rare) • Fainting (rare)
Minor		Tranexamic Acid: 
 • Stomach discomfort • Nasal congestion • Headache • Joint and Muscle Pain • Vision changes Venous blood draw: 
 • Discomfort at the needle site • Bruising • Clotting

Subject Safety and Data Monitoring:

Human Subjects Involvement and Characteristics:

We are proposing to enroll a total of 100 women into two study arms of 50 women each. Enrollment will be done exclusively at Parkland Hospital. Women who present for cesarean delivery will be screened by study team for eligibility. All women who volunteer to participate will sign a UTSW IRB-approved consent form and HIPAA authorization. Before being transported to the operating room, blood will be obtained by the study team for hematocrit (routine care), markers of fibrinolysis, & ROTEM analysis. The study team will then order “study drug” to be given:

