- 1) TXA 1 gram (diluted in 100 mL normal saline) given intravenously over 10 minutes, 10 minutes before skin incision *followed by* TXA 1 gram (diluted in 100 mL normal saline) given intravenously over 10 minutes at time of placental delivery.
- 2) Placebo (100 mL of normal saline) given intravenously over 10 minutes, 10 minutes before skin incision *followed by* placebo (100 mL normal saline) given intravenously over 10 minutes at time of placental delivery.

Parkland's *Investigational Drug Pharmacy* will prepare a blinded solution containing TXA or saline with a unique identifier according to a computerized randomization allocation sequence generated by [name] (statistician). The pharmacist on-call will deliver the solutions to an attending anesthesiologist. The study team which includes a research nurse will ensure that the solutions are infused per protocol. At delivery of the placenta & on postoperative day # 1, blood will be drawn for analysis of hematocrit, markers of fibrinolysis, & ROTEM by a study team member.

Sources of Materials:

Each participant will be assigned a unique study ID at enrollment. Blood samples collected from each participant will be appropriately labeled with the study ID number and will not contain patient identifiers. A master list linking the study ID with subject's information will be maintained by [name] on a secure, password-protected computer in his locked office with automatic saving to a secure, password-protected, backup hard drive. A Microsoft Access® database containing the collected information will be maintained separately on a secure, password-protected server that is accessible only within the University of Texas Southwestern. The database will not include protected health-care information. All information and material will be obtained for research purposes only and kept in strictly confidential. Any paper documents resulting from the study are kept in locked file cabinets accessible only by authorized research personnel.

Research material will include a total of 36 mL of **maternal** venous blood (twelve mL x three collections) and clinical information. Clinical information will be collected from the electronic medical record and direct patient interview. Collected information includes demographic information, medical and surgical history, physical examination, laboratory, imaging, and pathology reports.

Potential Risks:

The potential **maternal** risks involved in this study include:

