## **Statistical Analysis Plan**

Sample Size (total sample size=100, power 0.80, two-sided)

We selected a pilot of 20 patients randomly from schedule cesarean deliveries at Parkland Hospital. For this sample we performed the blood loss calculation for each delivery. This resulted in a mean blood loss of 2224 mL and a standard deviation of 362 mL. The trial is designed to observe a 205 mL reduction in the TXA arm over the placebo arms as from 2224 mL (placebo arm) to 2019 mL (TXA arm) with 80% power. This requires fifty patients randomized to each arm (one hundred total patients) using a two-sided test of significance level 0.05 using a Student's t-test.

Randomization was performed using a computer-generated table provided to the investigational drug pharmacy before patient recruitment. Randomization was according to randomized permuted blocks of size 6, 8, and 10. Data analysis included Pearson  $\chi^2$  for categorical data and Student's t-test for continuous data. P-values <0.05 were considered significant. Analyses were conducted with SAS version 4.1 (SAS Institute, Cary, NC).

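### The pre-infusion value of all eight Aim 2a fibrinolysis measures is collected but given no role in the analysis; ANCOVA would use it at almost no cost

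*Protocol*

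**What the plan says.** Under Specific Aims in the protocol, Aim 2a predicts that women given TXA "will have less evidence of fibrinolysis on measurement of serum markers and rotational thromboelastometry". Aim 2b concerns the next day, with the hypothesis "that by postoperative day 1, effects of TXA will have dissipated".

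The Methods for Aim 2 give the sampling times. For the four plasma markers (fibrinogen, PAI-1, t-PA, D-dimer) samples are "To be collected before initiation of infusion of TXA or placebo, at placental delivery, and on postpartum day 1". For ROTEM they are "To be collected before initiation of infusion, TXA or placebo, at delivery, and on postpartum day one", and the protocol adds that "we will compare ML values at 60 minutes, CT, CFT, and MCF values, numerically and graphically". That makes four plasma and four ROTEM measures, eight in all.

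Human Subjects Involvement and Characteristics confirms the draws. Before transport to the operating room, "blood will be obtained by the study team for hematocrit (routine care), markers of fibrinolysis, & ROTEM analysis". At delivery of the placenta and on postoperative day 1, "blood will be drawn for analysis of hematocrit, markers of fibrinolysis, & ROTEM by a study team member".

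The SAP names Pearson chi-square for categorical data. For continuous data it gives only the Student's "t-test for continuous data. P-values <0.05 were considered significant". Neither document mentions adjustment for baseline, change from baseline or a repeated-measures model.

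**The concern.** Each woman gives a pre-infusion value of every Aim 2a measure, and the plan does not say what is done with it. Two t-tests fit the wording: one on the delivery value, one on the change from pre-infusion to delivery. Their power can differ widely, depending on how strongly the two values are correlated. A third method, ANCOVA of the delivery value on arm and pre-infusion value, is at least as precise as either for practical purposes, whatever that correlation is.

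What is at stake is precision in a named secondary aim. The sample size was set for blood loss alone and no power is claimed for Aim 2, so with 100 women fixed, a baseline already in hand is the simplest source of extra precision. Validity is not at stake: between randomized arms either t-test keeps its 5% error rate.

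**Working it through.** **Inputs from the documents.** 50 women per arm; two-sided 0.05; Student's t-test. The primary design figures are a 205 mL difference and an SD of 362 mL.

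**Assumptions, not in the documents.** The correlation ρ between pre-infusion and delivery values (range 0 to 0.7), the treatment effect in SD units (0.3, 0.5, 0.7), equal SDs at both times, roughly normal data and no missing values.

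**The plan's own figure.** 205/362 = 0.566 SD. The standard error of a difference is √(2/50) = 0.2 SD, so the noncentrality is 0.566/0.2 = 2.83. With 98 degrees of freedom the power is 0.8006 (0.792 with 49 per arm). The stated 50 per arm for blood loss is reproduced. There is no corresponding figure for Aim 2.

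**Variance of the between-arm comparison, relative to the delivery-value t-test.**
- Delivery-value t-test: 1, with 98 df.
- Change-score t-test: 2(1 − ρ), with 98 df.
- ANCOVA: 1 − ρ², with 97 df. Estimating the slope multiplies this by about 1 + 1/96, shown in a separate column.

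Power is from the noncentral t with noncentrality effect/(0.2 × √variance).

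**Power at a 0.5 SD effect**

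| ρ | Delivery t-test | Change t-test | ANCOVA | ANCOVA with slope cost | ANCOVA simulated |
|---|---|---|---|---|---|
| 0 | 0.697 | 0.417 | 0.697 | 0.692 | 0.692 |
| 0.1 | 0.697 | 0.454 | 0.701 | 0.697 | 0.695 |
| 0.2 | 0.697 | 0.499 | 0.714 | 0.710 | 0.711 |
| 0.3 | 0.697 | 0.553 | 0.737 | 0.733 | 0.735 |
| 0.5 | 0.697 | 0.697 | 0.815 | 0.811 | 0.816 |
| 0.7 | 0.697 | 0.892 | 0.934 | 0.932 | 0.930 |

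The simulation used 40,000 trials per cell and allowed for chance baseline imbalance. Type I error was 0.047 to 0.051 for all three methods.

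**95% CI half-width in SD units** (t quantile × 0.2 × √variance, slope cost omitted)

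| ρ | Delivery t-test | Change t-test | ANCOVA |
|---|---|---|---|
| 0 | 0.397 | 0.561 | 0.397 |
| 0.3 | 0.397 | 0.470 | 0.379 |
| 0.5 | 0.397 | 0.397 | 0.344 |
| 0.7 | 0.397 | 0.307 | 0.283 |

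**Equivalent sample size.** To match ANCOVA with 50 per arm, the delivery-value t-test needs 50/(1 − ρ²) = 54.9, 66.7 and 98.0 women per arm at ρ = 0.3, 0.5 and 0.7. Allowing for the slope cost these become 54.4, 66.0 and 97.0.

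**Other effect sizes, ρ = 0.3, 0.5, 0.7.** At 0.3 SD the delivery-value t-test has 0.318 and ANCOVA 0.344, 0.403, 0.548. At 0.7 SD the t-test has 0.934 and ANCOVA 0.953, 0.979, 0.998.

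**Break-even.** With the slope cost included, ANCOVA equals the delivery-value t-test when (1 − ρ²)(1 + 1/96) = 1, that is at |ρ| of about 0.10. At ρ = 0 the loss is 0.697 − 0.692 = 0.005.

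**The case against.** The strongest reply is that nothing is wrong. An unadjusted t-test between randomized arms is unbiased, keeps its error rate and is a legitimate choice for a mechanistic secondary aim for which no power was promised. The gain depends on a correlation the documents do not give and which may differ among the eight measures; at 0.3 it is under four points of power. All of that is true, and it limits the point to efficiency. It does not remove the case for ANCOVA, because the choice does not require knowing the correlation: the most that can be lost is about 0.005 of power.

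The poor change-score figures also belong to a reading the documents never state. The ROTEM text speaks of comparing values, so the delivery-value t-test is the more natural reading, and against it the gain is the smaller one. This is fair. The change score matters only because the wording does not exclude it.

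Aim 2a names no time point of its own. Reading delivery as its time point is an inference from day 1 being assigned to Aim 2b. Day 1 has the same baseline available, so the same gap arises there. ANCOVA would not, however, turn a non-significant day 1 difference into evidence that the arms are comparable.

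Finally, the SAP describes the analysis in the past tense. If the comparisons have already been run, a switch to ANCOVA would be post hoc and should be labelled as such.

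**Conclusion.** The concern holds, as a recommended improvement rather than a correction. The plan collects a baseline for eight measures, assigns it no role and names a method that does not make efficient use of it. The silence in the documents and the low cost of the remedy are certain; the size of the gain is not. With 50 per arm and a 0.5 SD effect, power over the delivery-value t-test rises from 0.70 to 0.74, 0.82 or 0.93 if the correlation is 0.3, 0.5 or 0.7, and is practically unchanged if it is near zero. If a change-score t-test was intended, ANCOVA is better throughout this range, most clearly at low correlation. These figures rest on assumed correlations and effects and on roughly normal data. The blood-loss analysis and its sample size are not affected.

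**What to change.** In the SAP, replace the t-test for the eight Aim 2a delivery-time measures with wording such as:

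> *Each measure at placental delivery is compared between arms by ANCOVA, with arm and the woman's own pre-infusion value of that measure as covariate. The adjusted difference is reported with its 95% CI. A missing pre-infusion value is replaced by the overall baseline mean across both arms.*

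Where a measure is skewed and all its values are positive, log both the pre-infusion and delivery values and report a ratio. List the scale for each measure before the arms are compared, so that it is not chosen on the result. Leave the planned t-test for blood loss as it is.

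The cost is SAP wording, one degree of freedom per model and, at zero correlation, under 0.01 of power. The pre-infusion draw is already scheduled, so no samples or women are added. Without the missing-baseline rule, a woman lacking that value would drop out of the model.

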## **Statistical Analysis Plan**

Sample Size (total sample size=100, power 0.80, two-sided)

We selected a pilot of 20 patients randomly from schedule cesarean deliveries at Parkland Hospital. For this sample we performed the blood loss calculation for each delivery. This resulted in a mean blood loss of 2224 mL and a standard deviation of 362 mL. The trial is designed to observe a 205 mL reduction in the TXA arm over the placebo arms as from 2224 mL (placebo arm) to 2019 mL (TXA arm) with 80% power. This requires fifty patients randomized to each arm (one hundred total patients) using a two-sided test of significance level 0.05 using a Student's t-test.

Randomization was performed using a computer-generated table provided to the investigational drug pharmacy before patient recruitment. Randomization was according to randomized permuted blocks of size 6, 8, and 10. Data analysis included Pearson  $\chi^2$  for categorical data and Student's t-test for continuous data. P-values <0.05 were considered significant. Analyses were conducted with SAS version 4.1 (SAS Institute, Cary, NC).
